6.4.7.4 Medical Event of Interest Reporting

Selected non-serious AEs, as described in [Section 6.4.7.5](#), are classified as MEOIs and must be recorded as such on the AE CRF and reported to the sponsor via electronic media or on the paper MEOI Report Form. MEOIs that are identified from the date of first dose through 90 days following cessation of treatment, or 30 days after the initiation of a new anti-cancer therapy, whichever is earlier, need to be reported to the sponsor within 24 hours of the event in the same manner as outlined for SAEs (see [Section 6.4.7.3](#)).

Subjects should be assessed for the occurrence of possible MEOIs before administration of each dose of study treatment. Laboratory results should be evaluated, and subjects should be asked about any signs and symptoms experienced that are suggestive of an immune-related event. If laboratory test results or symptoms indicate possible immune-related MEOIs, then additional testing should be performed to rule out other etiologic causes. If no other cause is found, then the MEOI will be considered to be immune-related.

6.4.7.5 Definitions of Adverse Event

Adverse Event (AE)—Any untoward medical occurrence in a subject or clinical investigation subject administered a pharmaceutical product, medical treatment, or procedure, and which does not necessarily have to have a causal relationship with this regimen. An AE can therefore be any unfavorable and unintended sign (including an abnormal laboratory finding, for example), symptom, or disease temporally associated with the use of a medicinal product, medical

treatment, or procedure whether or not considered possibly, probably, or definitely related to the medicinal product. Progression of cancer is not considered an AE unless it is considered to be drug-related by the investigator.

Treatment-Emergent Adverse Event (TEAE)—Any AE that occurs, or an existing condition that worsens in severity, after administration of the first dose of the study drug.

Medical Event of Interest (MEOI)—Selected non-serious AEs are classified as MEOIs. The following treatment-emergent immune-mediated event is an MEOI for CMB305:

- Pneumonitis

As NY-ESO-1 is only detected in certain testicular cells in healthy individuals ([Gnjatic 2006](#)), the following male genitourinary-related events are MEOIs for CMB305:

- Prostatic pain
- Groin pain
- Testicular pain
- Epididymo-orchitis

MEOIs for this study include the following:

- An overdose of the sponsor's investigational product that is not associated with clinical symptoms or abnormal laboratory results
- Results from protocol-specified or unscheduled laboratory results showing simultaneous:
 - Increased ALT and/or AST $\geq 3 \times$ ULN,
 - Increased serum total bilirubin $\geq 2 \times$ ULN, without initial findings of cholestasis (elevated serum alkaline phosphatase) and
 - No other reason can be found to explain the combination of increased aminotransferase enzymes and total bilirubin, such as viral hepatitis A, B, or C; preexisting or acute liver disease; or another drug capable of causing the observed injury.

Note: These criteria are based upon available regulatory guidance documents.

The purpose of these criteria is to specify a threshold of abnormal hepatic test results that may require an additional evaluation for an underlying etiology. The site guidance for assessment and follow-up of these criteria can be found in the Investigator Trial File Binder (or equivalent).

During study conduct, additional new MEOIs may be identified by the Sponsor based on their clinical and laboratory features and understanding of underlying pathophysiology of the adverse events and will need to be reported as such. Such events may include dermatologic, endocrine, neurologic, gastrointestinal, respiratory and musculoskeletal toxicities, which are possibly

immune-mediated and possibly related to the study drug mechanism of action. Such adverse events may be delayed and wide ranging in terms of organs affected and severity.

Unexpected Adverse Event—An AE is “unexpected” when its nature (specificity), severity, or frequency are not consistent with the known or foreseeable risk of AE associated with the research procedures described in the protocol, Main Study ICF/assent form, or the Investigator Brochure.

Serious Adverse Event (SAE)—Any AE that results in any of the following outcomes:

- Death
- A life-threatening AE
- Inpatient hospitalization or prolongation of existing hospitalization

Note: Hospitalizations not to be reported as SAEs include admissions for planned medical/surgical procedure (such as scheduled tumor excision or debulking surgery) or routine health assessment requiring admission for baseline/trending of health status documentation (e.g., routine colonoscopy) or admission for social purposes such as lack of housing, economic inadequacy, caregiver respite, or family circumstances.

- A persistent or significant disability/incapacity
- Results in a congenital anomaly/birth defect
- Is a medically important condition that is judged by a health care professional as serious

The term “life-threatening” refers to an event in which the subject was at risk of death at the time of the event, and it does not refer to an event that hypothetically might have caused death if it were more severe.

Disability refers to a substantial disruption of a person’s ability to conduct normal life function.

- Medical and scientific judgment will be exercised in deciding whether expedited reporting is appropriate in other situations, such as important medical events that may not be immediately life-threatening or result in death or hospitalization but may jeopardize the subject or may require intervention to prevent one of the outcomes listed in the definition above. These may also be considered serious. Examples of such events are intensive treatment in an emergency room or at home for allergic bronchospasm; or blood dyscrasias or convulsions that do not result in hospitalization. For reporting in this study, any suspected transmission of an infectious agent via an investigational medicinal product is considered a serious adverse event.

When there is doubt regarding an AE meeting the criteria for an SAE, the investigator should default to reporting the AE as an SAE.

There are special circumstances in which an SAE reporting form is used to communicate important clinical trial safety observations that may not constitute an SAE.

- **Pregnancy:** Although pregnancy is not considered an SAE and is instead a normal human experience, all pregnancies reported in female subjects occurring in the month before or month after or occurring in female partners of male subjects in the month before or 3 months after for the last investigational injection must be reported to sponsor.
- **Overdose:** An overdose is defined as the accidental or intentional administration of any dose of a product that is considered both excessive and medically important. For reporting purposes, an overdose will be considered, regardless of adverse outcome, as an important medical event. All cases of overdose must be reported immediately to the sponsor.

6.4.7.6 Adverse Event Severity

All AEs will be evaluated according to the NCI-CTCAE v4.03 (2010) or newer (http://evs.nci.nih.gov/ftp1/CTCAE/CTCAE_4.03_2010-06-14_QuickReference_8.5x11.pdf) For AEs not listed in this reference scale, severity will be assessed by the investigator according to the criteria in Table 5.

Table 5 Adverse Event Severity Assessment

Grade 1 (Mild)	Mild; asymptomatic or mild symptoms; clinical or diagnostic observations only; intervention not indicated
Grade 2 (Moderate)	Moderate; minimal, local or noninvasive intervention indicated; limiting age-appropriate instrumental ADL ^a
Grade 3 (Severe)	Severe or medically significant but not immediately life-threatening; hospitalization or prolongation of hospitalization indicated; disabling; limiting self-care ADL ^b
Grade 4 (Life threatening)	Life-threatening consequences; urgent intervention indicated
Grade 5 (Death)	Death related to AE

ADL = activities of daily living; AE = adverse event

^a Instrumental ADL refer to preparing meals, shopping for groceries or clothes, using the telephone, managing money, etc.

^b Self-care ADL refer to bathing, dressing and undressing, feeding self, using the toilet, taking medications, and not bedridden.

Changes in the severity of an AE should be documented to enable an assessment of the duration of the event at each level of intensity. Adverse events characterized as intermittent require documentation of onset and duration of each episode.

6.4.7.7 Relationship

The investigator will report his or her interpretation of the relationship between an AE and the study treatment on the basis of their clinical judgment and the definitions in Table 6.

Table 6 Assessment of Relationship

Definitely related	AEs clearly attributable to study regimen administration
Probably related	AEs for which there is a reasonable possibility of causal association to study regimen
Possibly related	AEs for which there is confounding by comorbidities, medications or other considerations but for which it is not unreasonable that the AE may have been caused by study regimen. Note that it is not appropriate to invoke “you can’t rule it out.”
Not related	AEs that are considered clearly not causally related to study regimen, or for which there is a clear alternative explanation

AE = adverse event

If there is any question whether or not an AE is possibly, probably, or definitely related, the investigator should default to conservatism in categorization. Similarly, the investigator should default to conservatism by calling an AE an SAE if there is doubt regarding the serious nature of an AE, if it meets one of the definitions described above.

6.4.7.8 Clinical Laboratory Adverse Events

Clinically significant laboratory test results, in the opinion of the investigator, will be considered AEs and will be reported as shown in [Section 6.4.7](#).

It is the responsibility of the investigator to assess the clinical significance of all abnormal values as defined by the list of reference ranges from the local laboratory. In some cases, significant changes in laboratory values within the normal range will require similar judgment. An abnormal laboratory value that is not already associated with an AE is to be recorded as an AE only if any one of the following criteria is met:

- An action on the study drug is made as a result of the abnormality
- Intervention for management of the abnormality is required
- At the discretion of the investigator should the abnormality be deemed clinically significant

6.4.8 Pregnancy

Sexually-active men and FCBP must use a highly effective method of birth control during the course of the study, in a manner such that risk of failure is minimized. Before enrolling FCBP in this clinical trial, all FCBP must be advised of the importance of avoiding pregnancy during trial participation and for 30 days after the last dose of study drug administration and the potential risk factors for an unintentional pregnancy. Male subjects must be advised of the importance of their female partners avoiding pregnancy during the male subject's participation and for 3 months after the last dose of the study drug. All subjects (men and women) must sign an ICF documenting this discussion.

All FCBP must have a negative pregnancy test within 2 weeks prior to the study regimen initiation. If the pregnancy test is positive, the subject must not be enrolled in the study.

In addition, all FCBP should be instructed to contact the investigator immediately if they suspect they might be pregnant (e.g., missed or late menstrual period) at any time during study participation.

If following initiation of study dosing, it is subsequently discovered that a trial subject is pregnant or may have been pregnant within 1 month before or 4 months after, study regimens will be permanently discontinued, and the subject will be followed as possible by the investigator or designated health care professional to determine pregnancy outcomes for both mother and baby. If a male subject enrolled in study has a female sexual partner who becomes pregnant after initiation of the study, then the study subject should be asked by the investigator (or designated health care professional) for permission to approach his pregnant partner to follow-up to determine outcomes for both mother and baby.

6.4.9 HIV Screening Assessment

As part of study eligibility, subjects are required to have a negative HIV screening test at baseline. LV305 is an engineered lentivirus vector and is therefore derived from HIV. It is not known if treatment with LV305 will result in seroconversion of subjects to positive with HIV screening. Vectors derived from lentiviruses share some, but not all, of the proteins that are recognized in several screening blood tests for HIV. Secondary confirmatory assays such as Western Blot will demonstrate that the normal complement of HIV proteins is not present (unless, of course, the subject has developed true HIV infection). The informed consent document informs subjects regarding the possibility of positive HIV screening test after study treatment. Subjects enrolled in the study will be provided with a card from the study sponsor describing the possibility of a screening test becoming positive and the importance of confirmatory testing. In the event a study subject should have a screening HIV test performed and it returns a positive result, the site should inform and consult IMDZ for recommendations on the most appropriate confirmatory test to use.

6.4.10 Immune-mediated Events

While available data do not provide evidence of a causal relationship between CMB305 and the occurrence of immune-related events, a potential for such events exists because of the mechanism of action of CMB305. Investigators should promptly identify signs and symptoms of AEs representing an immunologic etiology and provide appropriate treatment. If an MEOI that is considered grade 2 or higher (with the exception of alopecia or vitiligo) occurs, subsequent doses of CMB305 should be withheld. CMB305 dosing should resume only after consultation with the sponsor.

The occurrence of any immune-mediated event will be evaluated by the data monitoring committee (DMC).

The immune-mediated event of pneumonitis will be captured as an MEOI; procedures for reporting MEOIs are provided in [Section 6.4.7.4](#).

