5.6.2 Treatment Delay

Administration of a study treatment component (LV305 or G305) will be delayed for the following adverse reactions:

- A drug-related non-hematological toxicity \geq Grade 2, with the exception of toxicity listed under requirement of permanent discontinuation of study treatment; Grade 2 fatigue alone does not require the withholding of study treatment;
- A drug-related hematological toxicity Grade 4.

Study treatment will resume according to schedule if drug-related toxicity improves to \leq Grade 1 within 4 weeks of onset. If Grade 2 toxicity stabilizes based on the investigator assessment (subject is asymptomatic and controlled), study treatment may resume after consultation with and approval by the Sponsor.

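### Sections 5.6.2 and 6.4.10 give incompatible restart instructions for a drug-related Grade 2 medical event of interest that recovers within 4 weeks

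*Protocol*

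**What the plan says.** Two sections of the protocol govern holding and restarting treatment after an adverse event that is also an MEOI.

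- **Section 6.4.10 (Immune-mediated Events).** The hold is: "If an MEOI that is considered grade 2 or higher (with the exception of alopecia or vitiligo) occurs, subsequent doses of CMB305 should be withheld". The restart is: "CMB305 dosing should resume only after consultation with the sponsor". There is no condition on drug-relatedness, no recovery grade and no time limit. The section names an event in its scope: "The immune-mediated event of pneumonitis will be captured as an MEOI".
- **Section 5.6.2 (Treatment Delay).** The hold is introduced by: "Administration of a study treatment component (LV305 or G305) will be delayed for the following adverse reactions". The listed reactions are drug-related non-hematological toxicity of Grade 2 or higher and drug-related hematological toxicity of Grade 4. There are two exceptions: toxicity that falls under permanent discontinuation, and Grade 2 fatigue alone. The restart is: "Study treatment will resume according to schedule if drug-related toxicity improves to" Grade 1 or lower within 4 weeks of onset. Sponsor consultation and approval appear only for Grade 2 toxicity that has stabilised without improving.

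Section 6.4.7.5 defines the class: "Selected non-serious AEs are classified as MEOIs". Pneumonitis is the listed immune-mediated entry ("The following treatment-emergent immune-mediated event is an MEOI for CMB305"), alongside male genitourinary events, overdose and a liver-test criterion. Section 5.6.3 sends severe or life-threatening drug-related events, and Grade 2 or higher events that do not improve over more than 4 weeks, to a discussion with the sponsor about permanent discontinuation. The SAP has no hold or restart rule.

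**The concern.** Both sections can apply to the same subject on the same day. The restart sentence in 5.6.2 is worded as an instruction. The one in 6.4.10 makes sponsor consultation a precondition. A site that follows 5.6.2 would restart without the check that 6.4.10 asks for. A site that follows 6.4.10 would wait for a consultation that 5.6.2 does not mention.

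Section 6.4.10 exists because the protocol expects that the mechanism of action could produce immune-mediated events. In a global trial, whether a subject is re-dosed after such an event with or without sponsor input should not depend on which section the site opened. There is also a smaller reporting consequence. Dose interruptions are to be summarised by arm (Protocol Section 7.8, SAP Section 8.3.6), and those summaries would mix two practices.

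**Working it through.** No sample size, event count or error rate enters this point, so the check is a comparison of text. The inputs are Protocol Sections 5.6.2, 5.6.3, 6.4.7.5, 6.4.10 and 6.5.2.

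**Step 1: do the two rules overlap?** Yes. MEOIs are non-serious events, and 6.4.10 applies from Grade 2. Section 5.6.2 applies from Grade 2 if the event is non-hematological and drug-related. A drug-related Grade 2 pneumonitis meets both conditions.

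**Step 2: does 5.6.2 exempt MEOIs?** No. One exception is fatigue of Grade 2 alone. The other is worded "with the exception of toxicity listed under requirement of permanent discontinuation of study treatment". Neither covers a recovering Grade 2 MEOI.

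**Step 3: apply both rules to each kind of Grade 2 or higher MEOI.**

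| Case | Section 5.6.2 (with 5.6.3) | Section 6.4.10 | Result |
|---|---|---|---|
| A. Drug-related Grade 2, Grade 1 or lower within 4 weeks | Hold, then restart on schedule; no sponsor step | Hold, then restart only after sponsor consultation | Direct conflict on restart |
| B. Drug-related Grade 2, stable but still Grade 2 | Restart needs sponsor consultation and approval | Restart needs sponsor consultation | Both involve the sponsor; approval is added in one |
| C. Drug-related, severe or life-threatening | 5.6.3: sponsor discussion on permanent discontinuation | Hold, then consultation | Both involve the sponsor |
| D. Grade 2 or higher, judged not drug-related | Not triggered; silent | Hold, then consultation | Different scope, no contradiction |

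**Step 4: is the overlap in case A settled elsewhere?** No. Neither section cites the other. Section 6.5.2 refers readers to Section 5.6 for discontinuation because of adverse events and does not mention 6.4.10. No section says which rule governs.

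**Step 5: what else differs?** Section 5.6.2 delays a component, LV305 or G305, although its restart sentence speaks of study treatment. Section 6.4.10 withholds CMB305. One requires drug-relatedness and the other does not.

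**Step 6: can the frequency be sized?** Not from these documents. The only information is in Section 1.1.2: no MEOIs among nine subjects at this LV305 dose in the earlier study. With 0 of 9, the one-sided 95% upper limit for the rate is 1 − 0.05^(1/9) = 0.283, or about 28%. That excludes very little. It also assumes that the earlier study defined MEOIs as this one does, which the documents do not say.

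**The case against.** The strongest reply is that 6.4.10 is the specific rule and 5.6.2 the general one, so a careful site would follow 6.4.10 for any MEOI. Safeguards also exist. MEOIs must be reported to the sponsor within 24 hours (Sections 6.4, 6.4.7.1 and 6.4.7.4), and subjects are to be assessed for possible MEOIs before each dose (Section 6.4.7.4). The sponsor should therefore know of the event before any restart.

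This lowers the practical risk but does not remove the contradiction. The protocol does not state that the specific rule prevails, and 5.6.2 lists its exceptions without including MEOIs. Notification is not consultation before restart, and nothing in the text links the two.

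The reply does defeat several stronger readings that a reader might infer:

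- *The sections conflict for every Grade 2 or higher MEOI.* They do not. Both hold dosing for a drug-related Grade 2 event, and cases B and C already reach the sponsor. In case C some looseness remains, because 5.6.2 speaks of a requirement to discontinue while 5.6.3 asks only that discontinuation be considered.
- *Section 5.6.2 tells sites to dose after an unrelated event.* It does not. It is silent on unrelated events, so a hold under 6.4.10 breaches nothing in it.
- *The alopecia and vitiligo exemption is empty because neither is on the MEOI list.* Section 6.4.7.5 lets the sponsor add MEOIs during the study and names dermatologic and other possibly immune-mediated events among the candidates. The exemption can apply to these.
- *The conflict can be measured by the doses that fall within a 4-week hold.* For drug-related Grade 2 events both sections impose the hold. What differs is the step before restart.

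**Conclusion.** The point holds in a narrow form. For a drug-related Grade 2 MEOI that improves to Grade 1 or lower within 4 weeks, the current protocol text gives two incompatible restart instructions and no means of choosing between them. The differences over relatedness and over component versus regimen are unclear scope, not contradictions.

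The conclusion rests on reading both sections as binding, since neither is marked as subordinate. No effect on the PFS or OS analyses is shown, and the number of subjects affected cannot be estimated. It should still be corrected, because it concerns re-dosing after a class of safety event that the protocol itself singles out. No view is taken on which rule is clinically right.

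**What to change.** Reconcile Sections 5.6.2, 5.6.3 and 6.4.10 and cross-reference them. The revised text should state:

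- whether MEOIs are governed by 6.4.10 or by 5.6.2;
- whether drug-relatedness matters for the hold;
- whether one component or the whole regimen is held;
- what must happen before dosing resumes.

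The sponsor's clinical team should choose the rule. The cost is protocol wording and cross-references. No assessment, sample size or analysis changes.

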6.5 Removal of Subjects from the Trial or Study Drug

Unless consent is withdrawn and the subject is unwilling to continue with safety follow-up, the subject is lost to follow-up, or the study is terminated, all efforts should be made to continue tumor and quality of life assessments as well as safety monitoring of all subjects.

Subjects who withdraw prior to the end of the study should be followed for new AEs for at least until 30 days after their last dose of study drug, i.e., CMB305. If the subject withdraws prematurely and is unwilling to continue safety follow-up, any subsequent SAE that may be causally related to study drug (i.e., CMB305) that comes to the attention of the site staff should be reported to IMDZ.

Information for long-term survival status should be obtained by any means, which includes, but is not limited to, public records where allowed by local authority, telephone contact, during an in-clinic visit, chart review, or via communicating with an individual (e.g., family, friend, referring health care provider) who is knowledgeable of the subject's survival status. More frequent survival status updates may be obtained at the request of the sponsor.

